The target sample size is 200 participants with 100 allocated to each group. Taking into account projected attrition of about 40 persons, we expect a final sample size of 240. Given our approach using multi-level longitudinal models (MLM) for these 200 subjects, 2 groups at 4 time points, we are 95% confident that power levels between 84% to 98% will achieve minimal detectable differences of 0.4 (within time and group by time) and 0.5 (between groups) (small-to-moderate effect sizes) for random effects subjects variance equal to 1. Covariate adjustments should further reduce variability and detectable effect sizes while increasing power. Additionally, to address the differences in proportion achieving virologic suppression and drug resistance, a chi-square test for a sample size of 200 yields a small-to moderate effect size (ω) of 0.1981 for 1 degree of freedom (2 x 2 table) at 80% power and 5% level of significance.

h.2 Plans for data management and analysis

h.2.a Data management Procedures for data management and monitoring will be initiated during the start-up phase. The project coordinator will coordinate the organization and processing of forms, and schedule and implement checks of data quality and completeness. Data from the ACASI files will be saved in the QDS data warehouse. Data will be backed up on a regular basis to prevent loss of data. Data will be transferred electronically from the sites to a secure password protected, HIPAA-compliant server at Emory University. A data-checking plan based on each questionnaire will be used to look for suspicious entries. Data monitoring will include scheduled checks for completeness every 2-4 weeks. Data sets from all assessment points will be merged as necessary to answer the research questions. Personal goals will be reported by the participant and typed into the database for qualitative analysis. They will be analyzed for the dimensions of content, specificity, effectiveness, and control. [name] will oversee the final quality assurance/quality control data reviews. She will design and conduct the statistical analyses; assist as with designing research forms and data entry; and collaborate with the

investigators on analysis and interpretation. We have successfully used these procedures with the pilot project and other research projects.

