Satisfaction (Aim 1) Two assessments will be conducted and analyzed to determine participant satisfaction with the mobile app in general, LN program and interactive manual. Both times, we will ask questions about likeability, usage rates, ease of use, acceptability, satisfaction, relevance, favorite song, understandability, and suggestions for improvement. The first assessment will entail observations and discussions with rural PLWHA while using the mobile app in focus group format. Observations and discussions will be recorded and content analyzed for themes, which will inform final revisions to the LN app. The second feasibility analysis will be the Program Evaluation Survey at the end of the study. Scaled responses to questions related to the above criteria will be analyzed using descriptive statistics and written comments will be entered into nVivo software and content analyzed for themes. We will also describe and evaluate the usage data from the web application designed to track app usage. We will determine average usage patterns and compare between groups (LN vs. EP).

Outcomes (Aim 2) All covariates will be evaluated to determine if any differences exist at baseline between the 2 groups (LN and EP), as well as testing for interactions (moderation) between groups and time. Inter-correlation among the covariates will also be evaluated. Multicollinearity diagnostics (variance inflation factors, tolerance, condition index) will be used to determine which covariates should remain in the subsequent models. MLM longitudinal models as detailed above will be used for each outcome (H1: adherence, H2: drug levels, and H3: CD4, viral load, drug resistance) to test differences between the 2 groups (group main effect), test for changes/differences from baseline to 3, 6 and 9 month (time main effect) and test for group by time effects (i.e. changes from baseline that are differences between the 2 groups) adjusting for significant covariates/moderators as needed. Appropriate link functions (e.g. logit, Poisson, other) will be assessed for each outcome within the MLM.

Exploratory outcome, mediators and moderators (Aim 3) Symptoms and symptom management scores will be examined using MLM as described above. Self-efficacy, outcome expectancy and personal goals are mediators in our model and meet the criteria for mediators as defined by Baron and Kenny⁴⁴

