and Bennett.⁴⁵ First, the intervention is designed to foster change in self-efficacy, outcome expectancy, and personal goals, and second, the mediators, in turn, are associated with the outcomes of adherence and symptoms. A number of authors have explicated the process by which mediation can be tested.^{46,47} A combination of statistical methods will be employed to determine the significance of mediation effects through the SPSS macro as described in Preacher and Hayes.⁴⁸ This SPSS macro runs the Baron and Kenny method and Sobel⁴⁷ test, as well as a non-parametric bootstrapping estimate, which is a more rigorous alternative to the Sobel test of the indirect effects. Based on the outcomes of these tests, each potential mediator will be assessed as to whether it provides for total, partial, or no mediation effect. Moderators such as depression and health literacy will be tested for main effects (differences at baseline) as well as for interaction (moderation effect) with the intervention (group) and across time. These moderation effects will be included within all mediation models to assess the extent of mediation of self-efficacy and outcome expectancy on adherence outcomes after adjusting for moderators and covariates.

Smartphone acceptance (Aim 4) Multivariate regression models will be used to address each hypothesis related to this aim. For Hypothesis 1, each antecedent (effort expectancy, performance expectancy and hedonic motivation) will be tested as a significant predictor of behavioral intent after adjusting for potential demographic covariates, such as age and gender. For Hypothesis 2, a simple regression model will assess the amount of association between behavioral intent and LN/EP app usage. For Hypothesis 3, multivariate regression will again be used to test for the moderating effects (i.e. two-way interaction effects) of smartphone experience and eHealth literacy on the association between the antecedents and behavioral intent. In place of traditional regression methods, the PROCESS plug-in macro for SPSS⁴⁹ will be employed using methods outlined by Hayes⁵⁰ to test the moderation effects of both smartphone experience and eHealth literacy on behavioral intention. (Note: for a continuous predictor variable and a continuous moderator variable, each will be mean-centered using the PROCESS macro before computing the interaction variable to avoid mathematically induced multicollinearity issues present for moderation testing.)

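### The Aim 2 model leaves its covariate rule open and neither conditions on nor constrains the baseline outcome: valid under randomisation, but it gives away precision

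*Combined protocol and SAP*

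**What the plan says.** Section h.2.b, Outcomes (Aim 2), sets out three steps.

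- Baseline comparison: "All covariates will be evaluated to determine if any differences exist at baseline between the 2 groups (LN and EP". The same sentence adds tests of interaction with group and time.
- Collinearity diagnostics, with no cut-offs, which "will be used to determine which covariates should remain in the subsequent models".
- A longitudinal mixed model for each outcome, with a group main effect, a time main effect, and a "test for group by time effects (i.e. changes from baseline that are differences between the 2 groups", "adjusting for significant covariates/moderators as needed".

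No Aim 2 covariate is listed. The general part of h.2.b sets 5% for every test, so a threshold exists, but not the test it applies to. Under Aim 3 the plan writes "Moderators such as depression and health literacy will be tested for main effects (differences at baseline", which hints that significant means imbalanced between arms but does not settle it for Aim 2. The age and gender named in h.2.b belong to Aim 4.

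Section h.1 describes the model as "2 groups at 4 time points", so baseline is one of the four modelled occasions. It claims 84% to 98% power for "minimal detectable differences of 0.4 (within time and group by time) and 0.5 (between groups" and adds: "Covariate adjustments should further reduce variability and detectable effect sizes while increasing power". It gives no R-squared, residual variance or within-person correlation.

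**The concern.** There are two separate issues.

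**Covariate rule.** Significant could mean a baseline difference between arms, an association with the outcome, or an interaction. Two competent statisticians could fit different models and both comply. If imbalance decides, a covariate enters by chance however prognostic it is, and the precision gain that h.1 counts on mostly disappears. If outcome association decides, little power is lost, but the set is chosen after outcomes are seen and can differ between outcomes. Nothing limits adjustment to pre-randomisation variables, since h.2.b cites time-varying covariates as an advantage of the model.

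**Baseline outcome.** Arm means at baseline are equal in expectation. A model that leaves them free and reads the effect as a difference in change behaves like a change-score comparison, which is less precise than conditioning on baseline. A group main effect averaged over all four visits has the opposite problem: one of the four visits precedes treatment and dilutes the effect.

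At stake are power from data already being collected, and whether the fitted model is determined by the plan or by the analyst.

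**Working it through.** **Inputs.** From h.1: 200 analysed, 100 per arm; 0.4 for group by time; 0.5 between groups; w = 0.1981 for the chi-square test. From h.2.b: 5% level (two-sided assumed). Assumed, because the documents give no values: total SD 1, compound symmetry with within-person correlation r = 0.3/0.5/0.7, covariate R-squared 0.05 to 0.40, and a constant effect at months 3, 6 and 9.

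**The plan's own figures.** w = (1.960 + 0.842)/√200 = 0.1981, as stated; 200 + 40 = 240, as stated. The 84% to 98% range can be neither confirmed nor refuted without the residual variance or r. A plain two-mean comparison gives 80.7% at 0.4 SD and 94.2% at 0.5 SD.

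**One follow-up visit, 0.4 SD.** The change contrast has variance 2(1−r) per person; conditioning on baseline gives 1−r². The ratio is 2/(1+r) = 1.54/1.33/1.18. Expected z = 0.4/√(variance × 2/100).

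| r | change: z, power | baseline-conditioned: z, power |
|---|---|---|
| 0.3 | 2.39, 67% | 2.96, 84% |
| 0.5 | 2.83, 81% | 3.27, 90% |
| 0.7 | 3.65, 95% | 3.96, 98% |

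**Joint 3-df group-by-time test, 0.4 SD at each visit.** Noncentrality is 6/(1−r) unconstrained and 24/[(1−r)(1+3r)] conditioned on baseline.

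| r | unconstrained | conditioned |
|---|---|---|
| 0.3 | 8.57, 69% | 18.0, 96% |
| 0.5 | 12.0, 84% | 19.2, 97% |
| 0.7 | 20.0, 98% | 25.8, 99% |

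**Group main effect, 0.4 SD after baseline.** Averaged over four visits the effect is 0.75 × 0.4 = 0.3, with variance (1+3r)/4: power 87/77/67%. The mean of the three follow-up visits, variance (1+2r)/3, gives 97/93/89%. Conditioned on baseline, variance (1+2r)/3 − r², it gives 99/99/99.9%.

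**Covariate selection, between-group comparison at 0.5 SD.** Simulation with one normal follow-up value, ten candidate covariates of which three are prognostic, selection at p < 0.05, 12,000 runs:

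| R-squared | unadjusted | imbalance rule | outcome-association rule | fixed three |
|---|---|---|---|---|
| 0.05 | 94.0% | 93.7% | 94.0% | 94.8% |
| 0.10 | 94.0% | 94.0% | 95.0% | 95.5% |
| 0.20 | 94.0% | 94.1% | 97.0% | 97.2% |
| 0.40 | 94.4% | 95.2% | 99.4% | 99.4% |

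Against the fixed set, the imbalance rule loses 1.1 to 4.2 points and the association rule 0 to 0.8. The imbalance rule picks a given prognostic covariate in about 5% of trials. The losses are small partly because power is near its ceiling. At 0.4 SD on one follow-up value, a second simulation gave 81–83% for the imbalance rule against 91–92% for a fixed set (R-squared 0.3) or 97% (0.5). The plan, however, attaches 0.4 to group by time, not to this comparison.

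**Type I error, normal outcome.** Imbalance rule 3.9–4.9%, association rule 4.9–5.2%, fixed set 4.8–5.3% in the first simulation; the imbalance rule fell to 3.0% at R-squared 0.5 in the second. If the most favourable of four readings (unadjusted, all covariates, imbalance-selected, outcome-selected) could be picked afterwards, it would be 8.2–8.8%.

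**Covariates and the linear group-by-time contrast.** With complete data and a random intercept, a time-invariant main effect explains variation between people, while this contrast is within people. Three simulated data sets (R-squared 0, 0.2, 0.4) gave identical month-9 estimates with and without three covariates, with standard errors agreeing to five decimals.

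**Binary outcome at w = 0.1981** (40.1% v 59.9% if pooled at 50%), latent R-squared 0.05/0.10/0.20/0.40: power about 82/82/81/82% under the imbalance rule and 82/84/86/91% with a fixed set. The same effect is an odds ratio of 2.23 unadjusted and 2.31/2.39/2.57/3.09 adjusted, so the covariate set also changes what a marginal logit model reports.

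**The case against.** The strongest reply is that nothing here is invalid. Baseline is already in the model, and the change contrast is unbiased under randomisation. At r = 0.5 and 0.7 the unconstrained 3-df test reaches 84% and 98%, inside the range h.1 claims. All of that stands. A reader might infer that the trial is underpowered against its own claim; the documents do not support this, because they give no correlation and the shortfall depends on an assumed low one.

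A reader might also infer that significance-based selection inflates type I error. Under any single mechanical rule it does not materially: binary null runs gave 4.2–5.4% for imbalance, 5.5–5.7% for association and 5.6–5.9% for the fixed set itself (Monte Carlo SE 0.3–0.4 points). The 8–9% figure needs a free choice between readings after the results are seen, which the text leaves possible but does not propose.

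Nor does covariate selection spoil every Aim 2 estimate. The linear group-by-time contrast is essentially untouched. In change-score simulations, adding clinic and ART entry route without baseline lowered power by 0.5 to 2.0 points compared with imbalance selection. The two issues must stay apart: the larger gains come from baseline, not from covariates.

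Finally, it is tempting to insist on clinic and entry route as covariates. No document shows either to be prognostic. One identical baseline term for all outcomes also fails for people initiating ART (section a.2), whose baseline pill count or hair level may be undefined or near zero. Both objections are accepted and shape the fix.

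**Conclusion.** The point holds as a loss of precision and an unfixed model, not as an invalid test. It should be corrected, but the trial does not depend on it.

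The main gain is from the baseline outcome: at 0.4 SD, 17, 10 and 2 points for one visit (84 − 67, 90 − 81 rounded from 90.4 − 80.7, 98 − 95) and 27, 13 and about 2 points for the 3-df test, at r = 0.3/0.5/0.7. The covariate rule costs about 1 to 4 points in the between-group comparison at 0.5 SD, only under the imbalance reading, and matters for non-linear models as well. Under the association reading the power cost is under 1 point, and the remaining fault is that the set is chosen after outcomes are seen.

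The sizes rest on assumed r and R-squared, compound symmetry, normal outcomes and complete data. Skewed pill-count and drug-level outcomes, which h.2.b expects, were not simulated. The interaction reading of the covariate rule was not quantified.

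**What to change.** Before any outcome is compared by arm, rewrite the Aim 2 model statement:

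1. In each model, estimate the treatment effect from the 3, 6 and 9 month values. Either keep baseline as a response with arm means constrained equal, or use it as a covariate, not both. State a convention for H1 and H2 in participants initiating ART who have no meaningful baseline pill count or hair level.
2. Delete selection by significance. Adjust for a short set of pre-randomisation covariates fixed in advance and chosen by the investigators on prognostic grounds. Depression score is one candidate, since the pilot results in b. Preliminary Studies link it to drug levels below the therapeutic range; clinic and ART entry route are optional. Name a reduced set for sparse binary outcomes such as drug resistance.
3. Report baseline balance descriptively, without tests, and leave moderator interactions to Aim 3.

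**Cost.** Mainly drafting, with no new visits or measures. Covariates that explain nothing cost under about 1 to 2 points of power: eight uninformative degrees of freedom cost 0.9 point between groups (93.6% to 92.7%) and 0.5 to 1.6 points on the baseline-conditioned contrast. Using baseline as a covariate drops participants without a baseline value unless a convention is set; the constrained form keeps them. If entry route is used, first confirm that the site tracking log records it for everyone, since Aim 5 describes it only for the first 106 participants.

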h.2.b Analysis Initial analysis will include descriptive statistics of sample characteristics (demographics, substance use, depression scores, etc. and CD4 and Viral Load.) and psychometric evaluation of all scored instruments. A combination of statistical software will be used for statistical analysis and data visualization, including SPSS (v.19), SAS (v. 9.2), and R (v. 2.13). Distributions, potential outliers, and patterns of missing data will be assessed to assure that the data meet assumptions for subsequent inferential tests. Missing data imputation methods may be used for small amounts (<5%) of missing data such that missing data are random. All statistical tests will be performed at the 5% level of significance, with exact p-values reported. Intent-to-treat procedures will be employed. For non-normal data, transformations may be performed to improve deviations from normality. However, it is well known that PC, viral loads and adherence measures are often skewed and experience floor and/or ceiling effects. Therefore, generalized linear models (GLM)/generalized estimating equations (GEE) frameworks will be employed as a more accurate reflection of the true underlying distributions generating these data. It is expected that logistic (logit)³⁷ and log-gamma³⁸ may be appropriate as well as Poisson, zero-inflated Poisson, and other link functions.^{39, 40} Additionally, it is expected that some attrition over time will occur. Mixed/multi-level models (MLM) will be used instead of repeated measures analysis of variance (RM-ANOVA) methods since MLM uses all available data (does not delete cases with missing values over time), handles data that are missing at random (MAR) which RM-ANOVA cannot, does not assume independence across time, provides a breakdown of variance both within and between subjects, and allows for both time-invariant and time-varying covariates.^{39, 40} It is expected that the majority of the analyses will occur in SPSS. However additional MLM and GLM/GEE models will be run using SAS (PROC MIXED, PROC NLINMIXED) and R (packages: LME4, GAMLSS as well as BRugs, which employs Bayesian estimation methods.⁴¹⁻⁴³

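### Aim 3 sorts mediators into total, partial or no mediation by 5% tests, but at 200 participants a non-significant direct effect is weak evidence that mediation is total

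*Combined protocol and SAP*

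**What the plan says.** Section h.2.b, under the Aim 3 heading, names self-efficacy, outcome expectancy and personal goals as mediators of the LN effect. "A combination of statistical methods will be employed to determine the significance of mediation effects", run through an SPSS macro that performs the Baron and Kenny method, the Sobel test and a non-parametric bootstrap of the indirect effect. From the results of these tests, "each potential mediator will be assessed as to whether it provides for total, partial, or no mediation effect". Moderator effects are to be included in all mediation models. Earlier in h.2.b: "All statistical tests will be performed at the 5% level of significance".

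Section h.1 sets the size of the trial: "The target sample size is 200 participants with 100 allocated to each group". It gives power for multilevel-model effects, with "minimal detectable differences of 0.4 (within time and group by time) and 0.5 (between groups"), and for a 2 x 2 chi-square test of virologic suppression and drug resistance. It gives none for a direct effect or for mediation. No section sets a margin, an upper bound on the direct effect, or a proportion mediated that would justify 'total'. The Specific Aims and h.2.b both present Aim 3 as exploratory.

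**The concern.** 'Total' mediation asserts that no part of LN's effect bypasses the mediator, so that the direct effect is zero. The three labels are to be assigned from significance tests. The Sobel test and the bootstrap can show that an indirect effect exists, but not that it is the whole effect. That leaves the direct-effect test within the Baron and Kenny steps, and a test of that kind reaches 'total' only through a non-significant result. Non-significance has that meaning only if the test would very probably have detected a direct effect worth caring about, and the plan does not examine this.

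Aim 3 is there to explain how LN works. A 'total' verdict for, say, self-efficacy would tell readers that nothing else in the program contributes, when a sizeable part of the effect might run by another route.

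**Working it through.** **The plan's own figures.** The chi-square figure in h.1 reproduces: (1.960 + 0.842)/√200 = 0.1981 at 80% power. The multilevel power range of 84% to 98% cannot be checked, because the residual variance and within-subject correlation are not given; it is not shown to be wrong. As a reference, a plain two-group comparison with 100 per arm and SD 1 has 80.7% power at 0.4 and 94.2% at 0.5. Neither stated figure concerns the direct effect.

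**Inputs.**
- From h.1: N = 200, 100 per arm; total LN effect d = 0.4 or 0.5, read as SD units.
- From h.2.b: 5% level. Sidedness is not stated; two-sided is assumed.
- LN effect on the mediator, a = 0.47 SD. This is the pilot self-efficacy effect size in Preliminary Studies (6.05/12.97). It is a change within the LN group, not a difference between groups, so it serves only as an illustration.
- Assumed, not in the documents: one outcome measurement per person, within-arm SD 1, and half of the total effect direct (c' = d/2), so that a·b = d/2.

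**Miss rate for the direct effect.** Mediator M = aX + e; outcome Y = c'X + bM + e, with residual variance 1 − b².
- R² of treatment on mediator = 0.25a²/(0.25a² + 1) = 0.0552/1.0552 = 0.052.
- SE(c') = √[(1 − b²)/(N × 0.25 × (1 − R²))], and 200 × 0.25 × 0.948 = 47.4.
- d = 0.4: b = 0.20/0.47 = 0.426; SE = √(0.819/47.4) = 0.131; power = Φ(0.20/0.131 − 1.96) = 33%; **miss 67%**.
- d = 0.5: b = 0.25/0.47 = 0.532; SE = √(0.717/47.4) = 0.123; power = Φ(0.25/0.123 − 1.96) = 53%; **miss 47%**.

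**Sensitivity.** With a between 0.4 and 0.8 SD, the miss rate is 64–73% at d = 0.4 and 40–59% at d = 0.5. Ignoring any precision gained from the mediator (SE = √(2/100) = 0.141), it is 71% and 58%.

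**How often 'total' would be assigned wrongly.** Half of the effect is truly direct, so every 'total' is false. Simulation with 20,000 trials per setting, N = 200, a = 0.47:

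| Reading of the label | d = 0.4 | d = 0.5 |
|---|---|---|
| Indirect effect significant, direct effect not | 61% | 44% |
| As above, and total effect significant | 46% | 39% |

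The second row adds the significant total effect that a strict Baron and Kenny sequence demands.

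**Could a margin rescue the label at this size?** The 95% interval for c' has a half-width of about 1.96 × 0.131 = 0.26 at d = 0.4 and 1.96 × 0.123 = 0.24 at d = 0.5. In simulation at d = 0.4 the mean was 0.26 and the smallest about 0.20. An interval that wide essentially cannot lie inside ±0.2, which is half of the 0.4 difference.

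**The case against.** Four points can be made for the plan.

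First, the rule is inferred. A reader might take h.2.b to say that 'total' means a non-significant direct effect, but it says only that labels follow from the test results. This stands: the criterion is unstated, and the rule used here is the natural reading of the named method. It does not remove the problem, because no other named test can separate total from partial, and an unstated criterion leaves the label to be settled after the data are seen.

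Second, the size depends on the scenario. A reader might infer that the test misses a half-sized direct effect two times in three. That fits a total effect near 0.4 SD. At 0.5, the plan's own between-group difference, it is about one in two. The rate of false labels also depends on whether a significant total effect is required. This stands, so ranges are given.

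Third, a reader might infer that a smaller sample makes 'total' easier to earn. Taken as an overall rate, it does not at a total effect of 0.4: the indirect effect must also be significant and loses power too, so false 'total' goes from 61% at N = 200 to 53% at N = 100 and 35% at N = 60. Only among trials with a significant indirect path does the share rise, from 68% at N = 200 to 82% at N = 100.

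Fourth, Aim 3 is exploratory, the planned bootstrap of the indirect effect is sound in itself, and covariates may add precision. All true, though the moderator terms in every mediation model may reduce precision. An exploratory aim is better served by estimates with intervals than by categorical verdicts.

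**Conclusion.** The concern holds in a limited form. The three-way label rests on 5% tests, and the only one that can support 'total' does so by failing to reject, with no bound and no stated power. When half of LN's effect is direct, that test misses it about 67% of the time at a total effect of 0.4 SD and about 47% at 0.5 SD, or roughly 40–73% over mediator effects of 0.4 to 0.8 SD. False 'total' labels follow in about 61% or 44% of trials, or 46% and 39% under the stricter reading. These figures rest on 100 per arm, a two-sided 5% test, SD 1, a single outcome measurement and an even split between direct and indirect effects; the 0.47 SD mediator effect is illustrative.

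A reader might go further and infer that the Aim 2 efficacy results are compromised. The documents do not support that: nothing in Aim 2 depends on the mediation labels.

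**What to change.** In the Aim 3 paragraph of h.2.b, replace the total/partial/no classification with this: for each mediator, report the indirect and the direct effect, each with a 95% bootstrap confidence interval, and state that a non-significant direct effect is not evidence of total mediation.

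An equivalence margin should not be added as a route back to the label without checking that it can be met; ±0.2 SD is effectively out of reach with 200 participants.

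The cost is one or two sentences of analysis wording, with no new data or visits. The downside is that a claim of total mediation will in effect not be available at this sample size.
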